9.4.1. Efficacy Analyses

9.4.1.1. Analyses of Primary Efficacy Endpoint

The primary analysis of the primary efficacy endpoint will be based on the Full Analysis Set (FAS).

For the LN cohort, proteinuria will be measured by UPCR in g/g derived from a single 24-hour urine collection at Screening and the mean of 2 separate 24-hour urine collections at Week 26.

For the IgAN cohort, proteinuria will be measured by absolute protein in g/day derived from the mean of 2 valid 24-hour urine collections.

To reduce skewness, the natural logarithm will be used to transform proteinuria values before analysis. An analysis of covariance (ANCOVA) will be used for the primary efficacy endpoint to compare reductions in proteinuria between the ravulizumab and placebo treatment groups. The ANCOVA model will include change from baseline in log-transformed proteinuria as the response variable and will adjust for baseline log proteinuria and the randomization stratification factor. The treatment effect will be evaluated using the least squares mean difference between treatment groups. The point estimate and two-sided 90% confidence interval (CI) for the mean difference of log-transformed proteinuria will be back-transformed (via exponentiation) to obtain the GMR and corresponding two-sided 90% CI. The values will then be expressed as percentage change in adjusted geometric mean of proteinuria at Week 26 relative to baseline.

For the LN cohort, data collected on or after receipt of additional standard of care therapy will be imputed using the proteinuria value from the 24-hour urine collection performed at the time of Renal Flare for the primary efficacy analysis. Additional sensitivity analyses will be performed to assess the impact of the missing data and assumptions.

For the IgAN cohort, participants initially randomized to the placebo group will receive ravulizumab in the Extension Period. Therefore, analysis of the secondary endpoints during the Extension Period will be summarized separately for each treatment group and baseline for the placebo group will be re-defined as the last measurement taken before the first dose of ravulizumab during the Extension Period (ie, the Week 26 measurement).

The primary efficacy endpoint analysis will also be performed on the Per Protocol Set.

Full details of these analyses will be provided in the SAP.

9.4.1.2. Analyses of Secondary Efficacy Endpoints

The secondary efficacy analyses will be descriptive in nature and will be based on the FAS.

9.4.1.2.1. Secondary Efficacy Analyses for Both LN Cohort and IgAN Cohort

- The percentage change from baseline in proteinuria at Week 50 will be analyzed using a mixed effect model for repeated measures (MMRM). The model will include change from baseline in log-transformed proteinuria as the response variable and fixed, categorical effects of treatment group, randomization stratification factor, visit, and treatment group by visit interaction as well as a fixed, continuous effect of baseline log proteinuria as a covariate. An unstructured covariance matrix will be used to model the correlations among repeated measurements within each participant. If this analysis fails to converge, a first-order autoregressive covariance matrix will be used. The Kenward-Roger approximation will be used to estimate denominator degrees of freedom.
- For the IgAN cohort, participants initially randomized to the placebo treatment group will switch to receive ravulizumab at Week 26. Therefore, the percentage change

from baseline in proteinuria at Week 50 will be summarized descriptively for each treatment group from the MMRM analysis and no formal treatment comparison will be made. For the LN cohort, the treatment effect will be evaluated using a contrast for treatment group-by-visit term at Week 50. The point estimate and two-sided 90% CI for the mean difference of log-transformed proteinuria will be back-transformed (via exponentiation) to obtain the GMR and corresponding two-sided 90% CI. The values will then be expressed as percentage change in adjusted geometric mean of proteinuria at Week 50 relative to baseline.

- The percentage of participants with > 30% and > 50% reduction in proteinuria at Week 26 and Week 50 will be summarized by treatment group by calculating the point estimate and two-sided 95% CI, based on exact confidence limits using the Clopper-Pearson method.
- The following endpoints will be summarized at baseline and each postbaseline time point by treatment group using descriptive statistics for the observed value as well as the change from baseline:
 - eGFR
 - Serum C3 and C4 concentrations

9.4.1.2.2. Secondary Efficacy Analyses for LN Cohort Only

The following secondary endpoints will be summarized by treatment group by calculating the point estimate and two-sided 95% CI, based on exact confidence limits using the Clopper-Pearson method:

- Percentage of participants meeting the criteria for CRR as well as individual components of CRR (defined in Section 3.2.5) at Week 26 and Week 50
- Percentage of participants meeting the criteria for PRR (defined in Section 3.2.5) at Week 26 and Week 50
- Percentage of participants with achieving corticosteroid taper (defined in Section 6.5.1) at Week 14, Week 26, and Week 50
- Percentage of participants with protocol-defined Renal Flare (defined in Section 3.2.1) through Week 50
- Percentage of participants with protocol-defined Severe Extrarenal SLE Flare (defined in Section 3.2.2) through Week 50
- Percentage of participants with Treatment Failure (defined in Section 3.2.4) through Week 50
- Percentage of participants with Suboptimal Response (defined in Section 3.2.3) through Week 50

Time to UPCR ≤ 0.5 g/g will be summarized based on spot urine samples. A Kaplan-Meier cumulative distribution curve will be generated for treatment group, and a log-rank test comparing the curves will be performed. The corresponding summary table will present by treatment group the cumulative distribution function (CDF) estimate, the number of participants

at risk, the number of participants responding, and the number of participants censored at each postbaseline time point. The table will also present the first quartile, median, and third quartile, along with two-sided 95% CI, of time to $UPCR \leq 0.5$ g/g.

Serum albumin will be summarized at baseline and each postbaseline time point by treatment group using descriptive statistics for the observed value as well as the change from baseline.

9.4.1.2.3. Secondary Efficacy Analyses for IgAN Cohort Only

The percentage of participants meeting the criteria for Partial Remission (defined in Section 3.2.6) at Week 26 and Week 50 will be summarized by treatment group by calculating the point estimate and two-sided 95% CI, based on exact confidence limits using the Clopper-Pearson method.

9.4.1.3. Multiplicity Adjustment

The secondary efficacy analyses will be descriptive in nature and no adjustment for multiplicity will be performed.

9.4.2. Safety Analyses

All safety analyses will be performed on the Safety Set and will be based on the actual treatment received.

9.4.2.1. Adverse Events

The following definitions will be used for AEs:

- Treatment-emergent adverse event (TEAE): Any AE that starts during or after the first dose of study drug. Adverse events that start 56 days or later after the last dose of study drug will not be considered as treatment emergent.
- Treatment-emergent SAE (TESAE): A TEAE that is serious

The incidence of TEAEs, TEAEs leading to withdrawal from the study, TEAEs leading to study drug discontinuation, drug-related TEAEs, and TESAEs will be summarized by treatment group for each disease cohort separately. All AEs will be coded using Medical Dictionary for Regulatory Activities (MedDRA) version 23.0 or higher and will be summarized by System Organ Class (SOC) and Preferred Term overall, by severity, and by relationship to study drug.

Detailed by-participant listings of TEAEs, SAEs, related TEAEs, TEAEs leading to withdrawal from the study, and TEAEs leading to study drug discontinuation will be provided.

9.4.2.2. Physical Examination and Vital Signs

Adverse changes from baseline in physical examination findings will be classified as AEs and analyzed accordingly.

Vital signs will be summarized descriptively by treatment group at baseline and postbaseline time points and for changes from baseline separately for each disease cohort.

9.4.2.3. Clinical Laboratory Tests

Observed values and changes from baseline in clinical chemistry, hematology, and urinalysis will be summarized descriptively by treatment group at baseline and at each postbaseline time point separately for each disease cohort. For laboratory results that can be classified as normal, low, or high based on normal range values, shifts from baseline in classification will be summarized for all study visits.

9.4.2.4. Electrocardiograms

By-participant data listings of ECG parameters will be provided separately for each disease cohort. Electrocardiograms will be evaluated and summarized as normal, abnormal not clinically significant, or abnormal clinically significant. A shift from baseline to worst on-study ECG table will be presented for ECG results. Observed values and change from baseline in ECG intervals (PR, RR, QT, and QTc) will be summarized descriptively at baseline and each postbaseline time point. The QT interval will be corrected for heart rate using Fridericia's formula (QTcF).

9.4.3. Pharmacokinetic/Pharmacodynamic Analyses

Graphs of mean serum ravulizumab concentration-time profiles will be constructed. Graphs of serum concentration-time profiles for individual participants may also be provided. Actual dose administration and sampling times will be used for all calculations. Descriptive statistics will be calculated for serum concentration data at each sampling time, as appropriate.

The PD effects of ravulizumab will be evaluated by assessing the absolute values and changes and percentage changes from baseline in serum free C5 concentrations over time, as appropriate. Descriptive statistics will be calculated for the PD data at each sampling time, as appropriate.

9.4.4. Immunogenicity Analyses

The incidence and titers for ADAs to ravulizumab will be presented at each postbaseline time point in tabular format separately for each disease cohort. Additionally, any confirmed ADA positive samples will be tested for the presence of neutralizing antibodies to ravulizumab.

9.4.5. Exploratory Analyses

9.4.5.1. Exploratory Efficacy Endpoints

The exploratory efficacy analyses will be descriptive in nature and will be based on the FAS. Full details regarding the exploratory efficacy analyses will be described in the SAP.

For continuous endpoints, data will be summarized at baseline and each postbaseline time point by treatment group using descriptive statistics for the observed value as well as the change from baseline.

For categorical endpoints, data will be summarized by treatment group by calculating the point estimate and two-sided 95% CI, based on exact confidence limits using the Clopper-Pearson method.

For the LN cohort, time to CRR, time to PRR, and time to UPCR > 50% decrease from baseline will be summarized using spot urine samples. Participants will be assigned as responders at the time of their CRR, PRR, or UPCR > 50% decrease from baseline, respectively, or censored at the

earliest of their discontinuation time, receipt of additional standard of care therapy, or at Week 50 if they have not responded or received additional standard of care therapy by then. Kaplan-Meier cumulative distribution curves will be generated for each treatment group, and a log-rank test comparing the curves will be performed. A corresponding summary table will present the CDF estimate, the number of participants at risk, the number of participants responding, and the number of participants censored at each postbaseline time point by treatment group. The table will also present first quartile, median, and third quartile, along with corresponding 2-sided 95% CI, of time to response.

Slope of eGFR for the IgAN cohort will be computed using a mixed effect model including data through Week 26 or Week 50, respectively. The model will include eGFR as the response variable, random patient effects for intercepts and slopes, fixed categorical effects of treatment group, visit, randomization stratification factor, and treatment group by visit interaction as well as a fixed, continuous effect of baseline eGFR.

9.4.5.2. Biomarkers

Analyses of exploratory biomarkers will be described in a separate SAP.

9.4.5.3. Quality of Life

The following quality of life assessments will be summarized by treatment group at baseline and each postbaseline time point using descriptive statistics for continuous variables for the observed value as well as the change from baseline:

- EQ-5D-5L
- SF-36 score
- FACIT-Fatigue (LN cohort only)

Additional details will be described in the SAP.

9.5. Planned Analyses

9.5.1. Dose Confirmation Analysis

To ensure the adequacy of the dose regimen, an interim PK/PD analysis for dose confirmation will be conducted by an independent clinical pharmacologist. The interim PK confirmation analysis will be conducted using masked PK/PD data from the first 10 participants treated with ravulizumab (a minimum of 3 participants in each disease-specific cohort), using data cut when the tenth participant reaches 2 weeks post first dose (ie, at Day 15). The PK dataset for review will include:

- Day 1 C_{max} , Day 15 C_{trough} , and C_{max} for all 10 participants.
- Pharmacokinetics data beyond Day 15 C_{max} timepoint (eg, Day 29 PK) may be included in the dataset (availability depending upon the enrollment rate).
- Free and total C_5 data associated with above timepoints and ADA data will be included in the dataset as supportive evidence.

If observed Day 1 C_{\max} , Day 15 C_{\max} and C_{trough} values, and other available PK/PD data are within the expected range, the study will proceed unchanged. If the totality of the available PK/PD data are not within the expected range, a dose regimen adjustment may be necessary for all participants or for a subset of participants. If all participants require a dose regimen adjustment, enrollment will be paused until a new regimen is determined. If dose regimen adjustment is only required for a subset of participants, enrollment may continue in the subset not requiring dose adjustment. In the event of dose adjustments, the participants treated with the previous dose will switch over to the new dose and continue treatment on study but will be excluded from the primary efficacy analysis. Replacement participants may be enrolled to preserve study power.

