6.8. Dose Modification

Dose modification of the study drug for an individual participant is not permitted for this study.

The adequacy of the dosing regimen will be confirmed through interim analysis of PK/PD data as described in Section 9.5.1. If the initial dosing regimen does not result in the anticipated PK/PD data, the dosing regimen may be modified for subsequent participants according to PK/PD data.

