9.3. Populations for Analyses

The following populations are defined for this study:

Population	Description
Randomized Set	All randomized participants. Participants will be analyzed as randomized for reporting disposition, demographics, and baseline characteristics.
Full Analysis Set (FAS)	All randomized participants who receive at least 1 dose of study drug. Participants will be analyzed as randomized for reporting efficacy data.
Modified Full Analysis Set (mFAS)	The mFAS is a subset of the FAS, excluding participants who were impacted by COVID-19.
Safety Set	All participants who receive at least 1 dose of study drug. Participants will be analyzed according to the study drug they actually received for reporting exposure and safety data.
Per Protocol Set	All randomized participants who receive at least 1 dose of study drug and without important protocol deviations.
Pharmacokinetic (PK) Analysis Set	All participants who receive at least 1 dose of study drug and who have evaluable PK data.
Pharmacodynamic (PD) Analysis Set	All participants who receive at least 1 dose of study drug and who have evaluable PD data.

Abbreviations: PD = pharmacodynamic; PK = pharmacokinetics

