4. ANALYSIS SETS

The following populations are defined for this study:

Analysis Set	Description
Randomized Set	All randomized participants. Participants will be analyzed as randomized for reporting disposition.
Full Analysis Set (FAS)	All randomized participants who receive at least 1 dose of the study intervention. Participants will be analyzed as randomized for reporting efficacy data.
Modified Full Analysis Set (mFAS)	
All FAS participants excluding participants who were impacted by COVID-19 as follows:
 
 1. Participants who received a dose of ravulizumab \geq 28 days after the scheduled dosing time point or missed a dose altogether during the 26-week Initial Evaluation Period due to COVID-19 2. Participants who withdrew from the study early during the 26-week Initial Evaluation Period due to COVID-19 3. Participants who received concomitant treatments for COVID-19 during the 26-week Initial Evaluation Period that could potentially affect efficacy 4. Participants who were hospitalized due to a COVID-19-related AE during the 26-week Initial Evaluation Period 
Inclusion in the mFAS will be determined for each participant prior to database lock.

Per-Protocol Set (PPS)	
All randomized participants who receive at least 1 dose of study intervention and without important protocol deviations who meet the following criteria:
 
 1. For LN cohort, satisfied the following inclusion criteria (IC)/exclusion criteria (EC): 
 – IC #10: Diagnosis of LN Class III or IV confirmed by biopsy – IC #12: Proteinuria with UPCR \geq 1 g/g based on one 24-hour urine collection during the Screening Period – EC #1: eGFR $<$ 30 mL/min/1.73 m² during Screening – EC #20: Received any of the specified treatments (see Protocol Section 5.2.2) 2. For IgAN cohort, satisfied the following inclusion/exclusion criteria: 
 – IC #13: Established diagnosis of primary IgAN based on kidney biopsy – IC #14: Mean proteinuria \geq 1 g/day on 2 complete and valid 24-hour urine collections during the Screening Period

Analysis Set	Description

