5.3. Primary Endpoint Analysis

The primary efficacy endpoint analysis will be based on the FAS.

The analyses for participants in the LN cohort and participants in the IgAN cohort will be conducted and reported separately. Participants in each disease-specific cohort will be analyzed as randomized, regardless of actual treatment received.

The randomization stratification factor will be based on strata verified by central laboratory and allowed concomitant therapy data from electronic case report forms (eCRFs). Sensitivity analysis may be performed using strata as randomized in IXRS (Interactive Voice/Web Response System).

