5.8. Interim Analyses

5.8.1. Dose Confirmation Analysis

To ensure the adequacy of the dose regimen, an interim PK/PD analysis for dose confirmation will be conducted by an independent clinical pharmacologist. The interim PK confirmation analysis will be conducted using masked PK/PD data from the first 10 participants treated with ravulizumab (a minimum of 3 participants in each disease-specific cohort), using data cut when the tenth participant reaches 2 weeks post-first-dose (ie, at Day 15). The PK dataset for review will include:

- Day 1 maximum concentration (C_{max}), Day 15 trough concentration (C_{trough}), and C_{max} for all 10 participants.
- PK data beyond Day 15 C_{max} timepoint (eg, Day 29 PK) may be included in the dataset (availability depending upon the enrollment rate).
- Total and free C_5 data associated with above timepoints and ADA data will be included in the dataset as supportive evidence.

If observed Day 1 C_{max} , Day 15 C_{max} and C_{trough} values, and other available PK/PD data are within the expected range, the study will proceed unchanged. If the totality of the available PK/PD data are not within the expected range, a dose regimen adjustment may be necessary for all participants or for a subset of participants. If all participants require a dose regimen adjustment, enrollment will be paused until a new regimen is determined. If dose regimen adjustment is only required for a subset of participants, enrollment may continue in the subset not requiring dose adjustment. In the event of dose adjustments, the participants treated with the previous dose will switch over to the new dose and continue treatment on study but will be excluded from the primary efficacy analysis. Replacement participants may be enrolled to preserve study power.

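### The dose-adjustment clause excludes participants from a primary analysis that is defined on the full FAS, and it does not say whether concurrent placebo participants are excluded too

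*Protocol*

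**What the plan says.** **The exclusion.** Protocol 9.5.1 provides for a masked PK/PD review by an independent clinical pharmacologist, based on the first ten ravulizumab-treated participants with at least three from each cohort. If the regimen is adjusted, those treated under the earlier dose "will switch over to the new dose and continue treatment on study but will be excluded from the primary efficacy analysis". Protocol 1.1 and 4.1 repeat this, as does SAP 5.8.1 ("In the event of dose adjustments, the participants treated with the previous dose will switch over to the new dose"). On replacement, the protocol says only: "Replacement participants may be enrolled to preserve study power".

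**The primary population.** Protocol 9.3 defines the FAS as "All randomized participants who receive at least 1 dose of study drug. Participants will be analyzed as randomized for reporting efficacy data". SAP 4 has the same rule: "All randomized participants who receive at least 1 dose of the study intervention". Protocol 9.4.1.1 uses the FAS for the primary analysis, and SAP 5.3 states: "The primary efficacy endpoint analysis will be based on the FAS". SAP 5.3 adds that analysis is as randomized, whatever treatment was received.

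**Who changes regimen.** Protocol 6.8 says "the dosing regimen may be modified for subsequent participants according to PK/PD data", and Protocol 4.3 also speaks of later participants. Protocol 4.1 and 9.5.1 have those already on treatment switch as well.

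**The concern.** There are two separate problems.

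First, one set of sections removes some participants from the primary efficacy analysis and another set keeps them in. If the clause were triggered, the choice of primary population would be open after randomization, and possibly after data had been seen.

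Second, the clause does not name the arm. If it removes only ravulizumab participants, the ravulizumab arm loses its early members and may gain later ones, while the placebo arm keeps its early members. The comparison is then no longer between groups randomized over the same period. Any drift over time in case mix, sites or background care would enter the treatment contrast on the primary endpoint.

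A further, conditional issue is the blind. Infusion volume is fixed by weight band (Protocol Table 9), and Protocol 8.6 uses volume as the blinded stand-in for dose when an overdose is suspected. If volumes or exclusion lists changed in one arm only, they would reveal the assignment. Under Protocol 6.3.2, participants unblinded in the Initial Evaluation Period are withdrawn.

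**Working it through.** **1. Is the exclusion implemented anywhere?**

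| Place | Treatment of a dose change |
|---|---|
| Protocol 1.1, 4.1, 9.5.1; SAP 5.8.1 | Excluded from primary efficacy analysis |
| Protocol 9.3, 9.4.1.1; SAP 4, 5.3 | FAS, no exclusion |
| SAP Table 1 (primary estimand) | Population is the FAS; the intercurrent events are additional standard-of-care therapy and treatment discontinuation only |
| SAP 4, Per-Protocol Set | No criterion for a dose change |
| SAP Appendix 5 (changes to planned analyses) | Lists only the hematuria change |

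No analysis set or estimand carries the exclusion. The conflict does not depend on how the arm question is read.

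**2. How many participants?** Ten reviewed, at least 3 in the other cohort: 10 − 3 = 7 in one cohort, and 7/40 = 17.5% of its ravulizumab arm. At 2:1 allocation about 7/2 = 3.5 placebo participants were randomized with them: 3.5/20 = 17.5%. Participants dosed after the tenth and before a decision would add to this. An adjustment limited to a subset would reduce it.

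**3. Bias if only ravulizumab participants are removed.** Let δ be the early-minus-late difference in log change that remains after the ANCOVA adjustment. The documents give no value, so 0.1 to 0.3 is assumed. The placebo arm keeps 17.5% early members and the ravulizumab arm has none, so the contrast shifts by 0.175 × δ.

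- δ = 0.1: 0.0175; exp(0.0175) = 1.018
- δ = 0.2: 0.035; exp(0.035) = 1.036
- δ = 0.3: 0.0525; exp(0.0525) = 1.054

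The planning standard error, with SD 0.60 and 10% dropout (36:18), is 0.60 × √(1/36 + 1/18) = 0.173. The shift is 0.0175/0.173 ≈ 0.1 to 0.0525/0.173 ≈ 0.3 standard errors. The planned effects are ln(0.85/0.55) = 0.435 (IgAN) and ln(0.60/0.40) = 0.405 (LN). If both arms are excluded over the same period, this shift is zero.

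**4. Power.** This is a one-sided two-sample t-test at 0.05 with noncentrality d / (0.60 × √(1/n₁ + 1/n₂)) and n₁ + n₂ − 2 degrees of freedom. The plan states approximately 80% in each cohort.

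| Randomized and kept (10% dropout then applied) | IgAN | LN |
|---|---|---|
| 40:20, everyone kept | 79.8% | 74.7% |
| 33:20, 7 ravulizumab removed, no replacement | 77.3% | 72.0% |
| 33:16.5, both arms removed, no replacement | 72.6% | 67.3% |

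The IgAN figure reproduces. The LN figure does not with the stated dropout; without dropout it is 78.6%. That shortfall is a separate matter, but it sets the LN baseline used here. Ravulizumab-only removal costs under 3 points, so its harm lies in validity rather than power. Symmetric removal without replacement costs about 7 points.

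**The case against.** The strongest reply is that the clause need not be arm-specific. Protocol 1.1, 4.1 and 6.1 call placebo infusions doses too, and Protocol 9.5.1 allows an adjustment for everyone or for a subset. Protocol 6.3.2 requires participants, sites and study staff to stay blinded through the Initial Evaluation Period, which fits a switch made in both arms. This stands as far as it goes: a reader might infer that the plan removes ravulizumab participants only, but the text does not settle it. That reading is the more natural one, because the paragraph concerns ravulizumab-treated participants and only they have a ravulizumab dose to change.

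A reader might also infer that the switch will break the blind. The documents do not support that. Table 9 matches placebo volume to ravulizumab volume in every weight band, and at Day 183 it adds placebo volume to equalize totals. Nothing prescribes a one-arm volume change. What is missing is a statement that the matching continues through a switch.

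The clause is contingent. The documents do not report the outcome of the dose confirmation review, and the amendment summaries list no ravulizumab dose change, so it may never have been triggered. It nevertheless remains in the protocol at Amendment 4 and in SAP version 4 (March 2025).

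Finally, Protocol 6.8 does not limit a modification to later participants in so many words. The sections may be incomplete rather than opposed, but they still need to be reconciled.

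**Conclusion.** The contradiction over the primary population is established from the text alone. The failure to say what happens to concurrently randomized placebo participants is equally plain. That removal is confined to ravulizumab is a probable reading, not a fact. The blinding risk arises only if volumes or exclusion lists change in one arm.

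The size is modest. Up to 7 of 40 ravulizumab participants from the first ten could be removed in one cohort, more if others are dosed before the decision. The possible shift of 1.8% to 5.4% in the geometric mean ratio, in either direction, rests on the assumed δ and on ravulizumab-only removal. It should not be read as an estimate of actual bias. The point should be corrected because it concerns the primary endpoint and is cheap to settle, but it does not undermine the trial as it stands.

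**What to change.** If the dose confirmation review has closed without a change, say so in the SAP and retire the clause. Otherwise amend Protocol 1.1, 4.1 and 9.5.1 and SAP 5.8.1 in one of two ways:

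- **Delete the exclusion** and keep the full FAS as randomized. This costs no participants. The estimate then averages over two regimens in the ravulizumab arm, which should be stated.
- **Keep an exclusion, but make it symmetric.** Define it by randomization date: all participants in the affected cohort and weight band, in both arms, randomized before the new regimen takes effect. Write it into the primary analysis set and add a full-FAS supplementary analysis. Commit to 2:1 replacement through the IRT, since replacement is now only optional, or restate the power (about 73% IgAN and 67% LN if 7 + 3.5 leave without replacement).

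In either case, state that any volume change applies to matching placebo, as in Table 9. Reconcile Protocol 4.3 and 6.8 with 4.1 and 9.5.1 on whether current participants also switch.

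The cost is protocol and SAP wording and an IRT instruction. Under the second option, add either the replacement participants or the loss of power.
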